#### 8. Compensation for time and effort:

Each patient will be compensated \$50 as per diem for travel expenses for the FACBC scan.

#### 9. Statistical Analysis and Power Calculation

In calculating statistical power we have taken realistic suppositions. The prevalence estimate of occult metastatic disease, FACBC sensitivity and specificity is extrapolated from reported large series and nomograms, as well as data culled from our previous trials and clinical experience [4, 5, 48, 52, 53]. The primary goal of the study is to estimate the rate of positive FACBC studies in this population for occult extraprostatic metastasis. We therefore assumed a 50% prevalence of occult metastasis (metastases not definitively evident on routine clinical imaging), 95% specificity, and a conservative sensitivity of 40%. They translate to 22.5% FACBC scans to be positive (note that FN included) and 89% PPV. We plan to enroll 88 patients to have 0.8 power for detecting the rate of positive FACBC to be at least 10%. The number of patients with positive FACBC is expected to be 20, and the number is between 12 and 28 with 0.95 probability. In addition to the point estimate, 95% CI will be calculated for the rate of positive FACBC and a statistical test will be conducted against the null hypothesis of a rate of 10%.

As part of the secondary analysis, we will cross-tabulate the FACBC classification versus extraprostatic disease status as detected by extended pelvic nodal dissection as outlined above. Note that the latter is not regarded as a gold standard for extraprostatic disease detection since it may still results in substantial false negatives. Nevertheless, the percent of positive FACBC among patients with extraprostatic disease detected by extended pelvic nodal dissection provides a reasonable estimate of the sensitivity for FACBC. We will calculate the corresponding exact 95% confidence interval. In addition, we will evaluate the extent to which the FACBC and extended pelvic nodal dissection agree with each other using kappa statistic. This analysis of concordance will help guide design of analyses of tissue-imaging concordance in the subsequent, Phase III Validation Trial (ECOG-ACRIN), to comprehensively evaluate the diagnostic characteristics of FACBC.

For Aim 2, we will assess associations between FACBC uptake parameters in the prostate and rate of extraprostatic disease detection using standard associative statistical tools including logistic regression and ANOVA as applicable.

For Aim 3, we will evaluate the association of the tissue RNA signatures of prostate cancer as well as urine and serum biomarkers with the rate of FACBC positivity using standard associative statistical tools including logistic regression and ANOVA as appropriate. Finally we will correlate FACBC uptake parameters in the primary prostate tumor to the tissue RNA signatures of aggressive prostate cancer and urine and serum biomarkers using Spearman's correlation coefficients.

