## 3. Objectives

## Primary Aim- To validate FACBC as an early indicator of occult metastatic disease among high risk or unfavorable intermediate-risk prostate cancer patients with presumed localized disease.

After completion of FACBC PET, detection rate for extraprostatic disease will be determined. In addition, after surgery and review of histology, correlation will be made to histologic findings for extraprostatic disease, as well as definitive skeletal imaging to determine diagnostic performance as a secondary analysis noted in the statistical analysis plan. Reference standards as to ground truth for extraprostatic disease will be established with histologic analysis of nodes harvested in extended nodal dissections, extrapelvic and/or skeletal biopsy and/or correlation with definitive imaging findings. Thus, for this aim: 1) positivity rate will be calculated for

FACBC PET for extraprostatic disease as the primary analysis; 2) diagnostic performance of FACBC in the detection of extraprostatic disease as confirmed with histology and/or correlative imaging will be determined as a secondary analysis.

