## 4. Study Design

We will undertake a clinical trial with 88 patients who have been diagnosed with primary prostate carcinoma who are considered at least unfavorable intermediate-risk (Grade Group 2 (Gleason score 3+4) with either PSA 10-<20 or clinical stage T2b-c, OR Grade Group 3 (Gleason 4+3) with PSA < 20) or high risk per standard guidelines (clinical T3a, or Gleason score 8-10, or PSA greater than 20 ng/ml; and/or recurrence probability of  $\geq$ 50%) as per clinical assessment, without definitive findings of systemic metastasis on conventional imaging, and who are candidates for potentially curable radical prostatectomy and extended pelvic nodal dissection. We will employ the Kattan nomograms and other standard instruments as appropriate in making this determination [48]. Subsequently, patients will undergo whole body FACBC PET-CT. Typically patients will then undergo radical prostatectomy and extended nodal dissection, but if disease is detected preoperatively outside of the prostate, this will inform a discussion between the surgeon and patient as to an individualized treatment plan which may include targeted nodal dissection and use of postoperative radiotherapy and/or systemic therapy. Primary analysis will be centered on detection of occult extraprostatic disease by FACBC PET in high or very high-risk patients without definitive findings of systemic metastasis on conventional imaging. While the primary endpoint will be FACBC PET occult extraprostatic disease detection, as a secondary analysis we will crosstabulate the agreement between FACBC classifications versus extraprostatic disease status as identified by extended pelvic nodal dissection and other extraprostatic truth verification. Patients will also be followed for long-term outcome, but that is beyond the scope of this current trial.

**FACBC radiolabeling:** Production will be accomplished by the GE FastLab cassette system. Alternatively by automated synthesis developed by [name] and [name] [49]. We have prepared greater than 200 batch productions for tumor imaging in volunteer subjects. Imaging will be performed under the IND held by [name] and FDA mandated monitoring will be completed.

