## Standard of Care Procedures

- 1. Conventional imaging: Prior to enrolment in this study, all patients will undergo standard of care preoperative bone scan and/or NaF PET, as well as nodal staging with diagnostic CT and/or MR per institutional standards. The official report is an important part of the initial evaluation and will serve as the basis for recording findings of extraprostatic disease since this will duplicate standard practice. Equivocal findings and/or non-definitive findings of systemic metastasis will be considered as negative for extraprostatic disease since management is typically not changed unless definitive radiologic findings are evident. The interpreter of the conventional imaging will have no access to FACBC imaging (and typically will be performed before FACBC). It is anticipated that all the conventional imaging will be reimbursed by third party payers.
- 2. Radical Prostatectomy and Extended Lymph node dissections: Patients will undergo standard of care radical prostatectomy and extended or super-extended pelvic node dissection. The surgical plan will generally involve nodal dissection of right and left obturator, right and left external iliac, right and left common iliac, right and left pre-sciatic, and central pre-sacral with optional para-aortic and para-caval regions subject to clinical exigencies. Each group of nodes will be removed as a packet, labeled separately and sent to pathology for routine histopathologic examination. If either conventional imaging or the FACBC scan demonstrates potential other pelvic or extrapelvic nodal disease, the surgeon may choose to extend the nodal dissection to other sites. If this is done, the additional nodes will be labeled to indicate the site and they will be also be submitted for pathology review. It is noted that some patients with extrapelvic disease may still undergo surgery after a discussion between patient and surgeon as to risks, advantages, and disadvantages since there is solid evidence that patients may still benefit from this approach [1-3, 11]. Burden of disease will likely be an important factor in this decision. In addition, since patient safety is paramount, an individual patient may have surgery stopped or altered due to clinical judgement, which will modify nodal basins sampled.

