After the FACBC scan described below, and before surgery the diagnostic imager and the surgeon will communicate to review findings and to ensure consistency in correlation of findings to nodal packet nomenclature. In addition, patients with abnormal though non-definitive findings on conventional imaging and/or abnormal and/or equivocal and/or discrepant on FACBC PET-CT in extraprostatic or especially extrapelvic locations may also have those sites sampled as clinically appropriate through a combination of percutaneous image guided needle biopsy and/or laparoscopic techniques.

3. Serum, urine, and tissue samples will be collected for RNA and other genomic analysis.

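### Section 9 judges FACBC against pelvic dissection alone while Sections 3 and 4 set a composite reference, so verified disease outside the dissected field is misclassified in the secondary analysis

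*Combined protocol and SAP*

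**What the plan says.** Section 9 gives three secondary statistics and ties each to dissection.

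- Cross-tabulation: "we will cross-tabulate the FACBC classification versus extraprostatic disease status as detected by extended pelvic nodal dissection as outlined above".
- Sensitivity: "the percent of positive FACBC among patients with extraprostatic disease detected by extended pelvic nodal dissection", with an exact 95% confidence interval.
- Kappa: "we will evaluate the extent to which the FACBC and extended pelvic nodal dissection agree with each other using kappa statistic".

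It adds that dissection is not a gold standard because it can miss disease. It also says the concordance analysis will help to design a later Phase III trial.

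Elsewhere the reference is wider. Section 3 (Primary Aim) establishes extraprostatic disease by "histologic analysis of nodes harvested in extended nodal dissections, extrapelvic and/or skeletal biopsy and/or correlation with definitive imaging findings". It also promises correlation with histology, "as well as definitive skeletal imaging to determine diagnostic performance as a secondary analysis noted in the statistical analysis plan". Section 4 (opening paragraph) describes the same cross-tabulation against disease status "as identified by extended pelvic nodal dissection and other extraprostatic truth verification". Section 4, Histologic Assessment, plans a comparison of nodal reads with histology by nodal group (item 1) and a separate comparison of skeletal reads with biopsy and correlative imaging (item 2).

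Section 4, Image Analysis, item 3 defines a positive extraprostatic read, and it covers both lymph nodes and bone.

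**The concern.** The two sides of the Section 9 table do not cover the same anatomy. The FACBC side is not limited to any site and includes bone. The reference side is whatever the nodal dissection removed. Two errors follow at patient level.

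First, a patient with a FACBC-positive bone lesion, confirmed by biopsy or concordant imaging, and negative dissected nodes is a true positive under Section 3 but a disagreement under Section 9. If FACBC misses such disease, the patient becomes an agreed negative.

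Second, a node-positive patient whose scan is positive only outside the dissected field counts as detected, although FACBC missed the nodes.

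Sensitivity and kappa are the only secondary accuracy or agreement statistics that Section 9 names, and the concordance results are meant to inform the next trial. With two references in the document, the choice between them could also be made after the results are seen.

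**Working it through.** **Inputs (Section 9):** 88 patients, prevalence 50%, sensitivity 40%, specificity 95%.

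**The plan's own figures.** Positivity = 0.5 × 0.40 + 0.5 × 0.05 = 0.225. PPV = 0.20 / 0.225 = 0.889. Expected positives = 88 × 0.225 = 19.8. These reproduce the stated 22.5%, 89% and 20.

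**Base table (composite reference).** With 44 diseased and 44 not: TP = 44 × 0.40 = 17.6; FN = 26.4; FP = 44 × 0.05 = 2.2; TN = 41.8. Observed agreement = (17.6 + 41.8) / 88 = 0.675. Chance agreement = (19.8 × 44 + 68.2 × 44) / 88² = 0.500. Kappa = (0.675 − 0.500) / (1 − 0.500) = 0.350.

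**Dissection-only reference.** Let e be the share of diseased patients whose disease lies only outside the dissected field, and s the FACBC sensitivity at those sites. The documents give neither, so both are assumptions. Overall sensitivity is held at 40%. Every patient is taken to be dissected, and dissection to find all disease in its field. Then:

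- TP = 17.6 − 44es
- FP = 2.2 + 44es
- FN = 44(1 − e) − TP
- TN = 41.8 + 44e(1 − s)

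| s | e | TP | FP | FN | TN | Sensitivity | Apparent PPV | Kappa |
|---|---|---|---|---|---|---|---|---|
| base | 0% | 17.60 | 2.20 | 26.40 | 41.80 | 40% | 89% | 0.350 |
| 40% | 10% | 15.84 | 3.96 | 23.76 | 44.44 | 40% | 80% | 0.333 |
| 40% | 20% | 14.08 | 5.72 | 21.12 | 47.08 | 40% | 71% | 0.315 |
| 40% | 30% | 12.32 | 7.48 | 18.48 | 49.72 | 40% | 62% | 0.293 |
| 70% | 10% | 14.52 | 5.28 | 25.08 | 43.12 | 37% | 73% | 0.270 |
| 70% | 20% | 11.44 | 8.36 | 23.76 | 44.44 | 32.5% | 58% | 0.180 |
| 70% | 30% | 8.36 | 11.44 | 22.44 | 45.76 | 27% | 42% | 0.078 |

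Worked row (s = 40%, e = 30%): agreement = (12.32 + 49.72) / 88 = 0.705; chance = (19.8 × 30.8 + 68.2 × 57.2) / 88² = 0.5825; kappa = 0.1225 / 0.4175 = 0.293.

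In the 40% rows sensitivity holds because numerator and denominator shrink together (39.6, 35.2 and 30.8 diseased patients instead of 44). In the 70% rows it falls because the in-field disease that remains is, by construction, detected less often. That figure correctly describes the dissected field but not FACBC for extraprostatic disease as a whole.

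**Hits outside the field in node-positive patients.** Suppose all 44 diseased patients are node-positive and, by assumption, 20% of the 17.6 hits are positive only outside the field. Section 9 still reports 40%. Matched to the field, TP = 17.6 × 0.8 = 14.08 and sensitivity = 14.08 / 44 = 32%. Kappa = ((14.08 + 41.8) / 88 − 0.500) / 0.500 = 0.270.

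**The case against.** The case for leaving the text alone has real substance.

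- **Kappa is declared as agreement between two named methods.** If FACBC is positive in bone and the nodes are negative, the two methods do disagree. This stands: kappa is not wrongly computed. But it sets a whole-body read against a regional procedure, so part of the disagreement comes from coverage alone.
- **Dissection as the reference for sensitivity looks deliberate.** Histology is a defensible denominator, and Section 9 admits that dissection misses disease. The admission changes no classification, however. The related limitation in Section 7 concerns missed nodes, not bone.
- **The closing words of the cross-tabulation sentence may import Section 4.** Possibly so for the table. The sensitivity and kappa sentences name dissection without those words, so table and statistics would then use different references.
- **Section 4, Histologic Assessment, already plans site-specific comparisons.** True, but Section 9 carries neither forward.
- **Dissection can go beyond the pelvis.** Section 4, Standard of Care Procedures, item 2 has optional para-aortic and para-caval regions, and "the surgeon may choose to extend the nodal dissection to other sites". Some extrapelvic nodes are therefore covered, and bone is the main gap.

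A reader might also infer that a positive FACBC result is undefined. It is not: Image Analysis, item 3 defines it, and only a site restriction is missing. Nor do the documents show that accuracy will be biased in a known direction. Sites flagged by FACBC "may also have those sites sampled as clinically appropriate", and some patients may not have surgery (Section 5, Dropout). Those are separate gaps in detail, and nothing in the documents fixes their net effect.

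**Conclusion.** Section 9 conflicts with Sections 3 and 4 on the reference for the secondary analysis and, followed literally, misclassifies patients whose verified disease or FACBC uptake lies only outside the dissected field.

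The size depends on shares that the documents do not give. With extrapelvic-only disease in 10% to 30% of diseased patients, kappa moves from 0.35 to 0.33-0.29 if FACBC sensitivity is equal at all sites, and to 0.27-0.08 if it is 70% at those sites. Sensitivity is unchanged in the first case and 37-27% in the second. PPV is not named as a secondary statistic in Section 9, but it can be read from the table.

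Many of these shifts are within sampling error at this size: the exact 95% interval for 18/44 is 26% to 57%, and the approximate interval for the base kappa is 0.19 to 0.51. The intervals do not account for misclassification.

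A reader might infer that the trial's main result is at risk. It is not: the primary endpoint is the FACBC positivity rate, which uses no reference standard.

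**What to change.** Reconcile Section 9 with Sections 3 and 4 by specifying two patient-level analyses.

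1. **Diagnostic performance:** FACBC positive at any extraprostatic site against the Section 3 composite (nodal histology, biopsy, definitive imaging). This also supplies the skeletal comparison that Section 3 says is in the SAP.
2. **Agreement in the dissected field:** sensitivity and kappa against dissection histology, counting only FACBC reads within the nodal regions actually dissected, and labelled as FACBC-versus-dissection agreement in that field.

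The cost is analysis wording. Nodal packets and FACBC nodal reads are already labelled by region (Section 4, Standard of Care Procedures, item 2, and Histologic Assessment, item 1). Keeping both analyses at patient level avoids correlated regions within a patient.

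The downside is a possibly less favourable sensitivity in (2). In both analyses, what gets verified still depends partly on the FACBC result, more so in (1), where FACBC findings can prompt biopsy. The plan should state this as a limitation.

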## 5. Participant selection

- 1) Inclusion criteria
  - a. High-risk or very-high risk prostate cancer eligible for standard of care surgery
    - i. At least clinical T3a disease, and/or Gleason >8, and/or PSA>20, as per clinical assessment and routine guidelines
  - b. Unfavorable risk intermediate prostate cancer eligible for standard of care surgery
    - i. Grade Group 2 (Gleason score 3+4) with either PSA 10-<20 or clinical stage T2b-c, OR Grade Group 3 (Gleason 4+3) with PSA < 20.
  - c. 18 or years of age or older
  - d. Undergone standard of care conventional imaging (CT and/or MR; bone scan and/or NaF PET)
- 2) Exclusion criteria
  - a. Definitive findings of systemic metastasis on conventional imaging.
- 3) Recruitment: Any attempt to recruit a large cohort of subjects is always a possible limitation. We believe with the typical numbers of patients for this clinical question seen at Emory hospitals including ESJH hospital per year (approximately 50), we will be able to achieve our target goal of 18 patients per year at a conservative 36% recruitment rate. We have an on-site cyclotron and radiopharmacy staff with a proven ability to manufacture FACBC. Thus, we have the capacity to scan these subjects. If accrual is lagging, we also have the capability to open this trial at our sister institutions, Grady Hospital and the Atlanta VA.
- 4) Dropout: We have factored in an extra 2 scans for unforeseen difficulties, but since the endpoint of the study is FACBC imaging, even if a patient does not undergo surgery, sufficient data will have been obtained for the primary analysis. Therefore patient dropout is not considered to be highly relevant in this design. We will seek IRB approval of sufficient patients to allow for screening failures, but these patients will not have undergone FACBC imaging.

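### FACBC sensitivity is estimated only in men with dissection-proven disease, while the scan can influence who is dissected and where, so it may be biased in an unknown direction

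*Combined protocol and SAP*

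**What the plan says.** The secondary analysis in Section 9 cross-tabulates FACBC against dissection findings and states that FACBC positivity among men with dissection-detected disease "provides a reasonable estimate of the sensitivity for FACBC". An exact 95% interval and a kappa accompany it. Section 9 concedes that dissection is not a gold standard and may miss a substantial amount of disease. It gives no rule for men who are not dissected.

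Other sections describe how the FACBC result can enter the verification process:

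- **Who is operated on.** Section 4 (Study Design) has extraprostatic findings feed into a discussion of individual treatment between surgeon and patient. Standard of Care Procedures says that some men with extrapelvic disease may still have surgery, which implies that others may not. Section 5 (Dropout) foresees unoperated men but covers only the primary endpoint: "even if a patient does not undergo surgery, sufficient data will have been obtained for the primary analysis".
- **Where disease is looked for.** If conventional imaging or FACBC suggests further nodal disease, "the surgeon may choose to extend the nodal dissection to other sites". Imager and surgeon review the scan together before surgery, and Histologic Assessment says that the FACBC reads guide both dissection and labelling.
- **What counts as truth.** The Primary Aim in Section 3 adds "extrapelvic and/or skeletal biopsy and/or correlation with definitive imaging findings" to nodal histology. Section 4 also mentions other verification alongside dissection. The Section 9 sensitivity sentence names dissection alone.

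**The concern.** A man without a dissection cannot enter the denominator of the Section 9 sensitivity. If FACBC-positive men with disease are operated on less often, true positives drop out and the estimate falls. If FACBC-positive sites are dissected more thoroughly, disease is confirmed more readily in FACBC-positive men and the estimate rises. Neither effect shows in an exact interval, which describes sampling error around whatever proportion the verification process produces.

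The conceded false negatives are a different problem. Misses that are equally frequent in FACBC-positive and FACBC-negative men leave this ratio unchanged. What matters is unequal verification, and Section 9 does not mention it. Section 7 discusses only the case where FACBC-positive nodes are missed at dissection and the false-positive rate is overstated.

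At stake are a secondary estimate of diagnostic performance and the kappa. Section 9 says that the concordance analysis will help design similar analyses in a later validation trial.

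**Working it through.** **Plan's own figures.** Inputs from Section 9: N = 88, prevalence 50%, sensitivity 40%, specificity 95%.

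- Positivity: 0.5 × 0.40 + 0.5 × 0.05 = 0.225.
- PPV: 0.20 / 0.225 = 0.889.
- Expected positives: 88 × 0.225 = 19.8.

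These agree with the plan: "They translate to 22.5% FACBC scans to be positive (note that FN included) and 89% PPV", and about 20 positive scans. Expected diseased men: 88 × 0.5 = 44, of whom 44 × 0.40 = 17.6 are FACBC-positive and 26.4 FACBC-negative.

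**Estimator under unequal verification.** Let v be the probability that a diseased man is dissected and d the probability that dissection finds his disease, with + and − for the FACBC result. The planned ratio has expectation of about

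Se·v₊·d₊ / [Se·v₊·d₊ + (1 − Se)·v₋·d₋],

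which equals Se only if v₊·d₊ = v₋·d₋. The documents give none of these four quantities. The values below are assumptions, with v₋ = 1 throughout.

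| Assumed scenario | Calculation | Apparent sensitivity (truth 40%) |
|---|---|---|
| All dissected, equal yield 0.8 | 14.08 / (14.08 + 21.12) | 40% |
| 4 FACBC-positive diseased men skip surgery, full yield otherwise | 13.6 / (13.6 + 26.4) | 34% |
| All dissected, yield 0.9 in FACBC-positive and 0.7 in FACBC-negative men | 15.84 / (15.84 + 18.48) | 46% |
| 4 skip surgery, yield 1.0 and 0.77 | 13.6 / (13.6 + 20.33) | 40.1% |

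In the last row v₊ = 13.6 / 17.6 = 0.77, so the two effects cancel. Harsher inputs with one mechanism at a time widen the range. If half of the FACBC-positive diseased men skip surgery at full yield, the result is 8.8 / 35.2 = 25%. If all are dissected with yields of 0.9 and 0.5, it is 15.84 / 29.04 = 54.5%.

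**Scale.** Rounding 17.6 to 18, the exact 95% interval for 18/44 is 26% to 57%. The 34% and 46% results both lie inside it, so the possible bias is smaller than the sampling uncertainty in these cases, but the interval does not account for it.

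**What bounds can and cannot do.** With 4 undissected FACBC-positive men, counting none and then all as diseased gives 13.6/40 = 34% and 17.6/44 = 40%, which contains the truth. In the 0.9 and 0.7 case nobody is undissected, so bounds of this kind collapse to 46% and miss it.

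**The case against.** A reader might infer that the estimate *is* biased, or biased in a stated direction. The documents do not support that. The two routes oppose each other, no share of men skipping surgery and no yield by FACBC result is given, and plausible combinations cancel. Section 4 also says that patients will typically go on to surgery. Losing 4 of 17.6 men (23%) is an illustration, not a forecast.

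The effect of FACBC-directed extra sites is also limited at patient level. The standard operation already covers nine named packets. An extra site changes a man's status only if every template packet is negative and the extra site is positive, and conventional imaging can prompt extension as well.

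The wider reference standard is not absent: Sections 3 and 4 describe it, and Section 9 refers back to what was outlined earlier. Finally, Section 9 ties the concordance analysis to the design of later concordance work. It does not say that this sensitivity figure will set assumptions for that trial.

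All of this stands, and it limits the claim to possible bias of unknown sign. It does not rescue the description of the figure as a reasonable estimate of sensitivity. That needs v₊·d₊ and v₋·d₋ to be about equal, and the plan neither argues nor checks this.

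**Conclusion.** The point holds as a risk, not as a demonstrated bias. Section 4 allows verification to depend on the FACBC result, Section 9 neither acknowledges nor handles this, and the resulting sensitivity and kappa may be off in either direction. On the assumed inputs the apparent sensitivity moves from 40% to 34% or 46%, or stays at about 40% when the mechanisms offset each other. Kappa was not recomputed, because that needs further assumptions.

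Two stronger inferences should be resisted. First, the primary analysis is not affected: every scanned man contributes to the positivity rate whether or not he has surgery. Second, moving wholesale to the composite reference would not solve the problem. Biopsy and additional sampling are prompted by suspicious sites, including FACBC-positive ones, so a composite would tend to add FACBC-positive disease and could push the estimate up. This should be corrected in the analysis plan, but it does not bear on the validity of the main result.

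**What to change.** Amend the secondary analysis in Section 9. Nothing about surgery or patient management needs to change.

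1. Reconcile Sections 3, 4 and 9 on which reference standard applies to which estimate.
2. Tabulate all scanned men by FACBC result against three outcomes: dissection-positive, dissection-negative and not dissected. Report sensitivity and PPV with bounds that count undissected men as all diseased and as none diseased. Set these separately in FACBC-positive and FACBC-negative men, because the extremes for sensitivity come from opposite assignments in the two groups.
3. Base the main dissection comparison on the standard-template packets only. Report FACBC-directed extra sites and the composite reference (biopsy, definitive imaging) separately, stating that these are sought more often in FACBC-positive men.
4. Label the dissection-only figure *positive agreement with dissection*. State that neither the bounds nor the template restriction removes unequal yield within the template, since the reads may guide dissection there too.

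The protocol already has packets and additional sites labelled separately, so no new patients or procedures are needed. The cost is revised wording, a few extra tables, and wider and less favourable intervals.
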